### **Measurement of outcomes**

Five types of JA of our interest will be identified in HQMS, including KA, HA, SA, EA and AA. Epidemiological characteristics, risk factors, complications and resource utilization of these five types of JA will be analyzed.

## **Statistical analysis**

Line charts will be drawn to describe annual change in trends of JA. Basic information in different groups will be compared. For continuous variables, Mann-Whitney U test will be used for non-normally variables and Student t-test will be used for normally variables, while chi-square test or Fisher's exact test will be used for categorical data. Then, multivariable-adjusted logistic regression will be performed to examine the risk factors of complications following JA (e.g., year of surgery, patient demographics and region of hospitals) with the calculation of odds ratios (ORs) and 95% confidence interval (CI). To minimize the effect of potential confounders, the propensity-score matching or multivariable-adjusted regression will be performed to compare the incidence of complications and resource utilization in different groups.

SAS 9.4 (SAS Institute Inc., Cary, NC, USA) will be used in all statistical analyses and  $P < 0.05$  will be considered as significant.

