## **Introduction**

Joint arthroplasty (JA) is a safe and cost-effective musculoskeletal surgical procedure for relieving pain and improving function and health-related quality of life for patients with end-stage joint disease. As one of the most commonly performed procedures, more than 1.5 million knee arthroplasties (KA), more than 1 million hip arthroplasties (HA) and over 100 thousand shoulder arthroplasties (SA) were performed annually worldwide. In addition, more than 10 thousand elbow arthroplasties (EA) in Germany and has been rapidly increasing. Moreover, the incidence of ankle osteoarthritis has been estimated to be 47.7/100,000, affecting approximately 1% of the world population. The increased demands of JA pose a challenge for the health care system from a quality and finance perspective.

China is the most populated country in the world, and now has the second-largest economy in the world. As nearly 420 million Chinese are aged more than 50 years, and the living standards and health system continue to improve, the demand for healthcare, including JA, is increasing. However, the consequences of increased access to new medical technologies and their application to patient care is unknown. Description of epidemiological characteristics, risk factors, complications and resource utilization of JA, can provide valuable information for healthcare planners in China and similar countries, and can guide care providers to develop effective and targeted preventive measures to minimize mortality from this procedure.

Therefore, in this study, investigators will use data from a mandatory patient-level

national database, i.e., the Hospital Quality Monitoring System (HQMS), to study the epidemiological characteristics, risk factors, complications and resource utilization of JA (i.e., KA, HA, SA, EA and ankle arthroplasty [AA]).

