### **Study variables**

Patient demographics (e.g., age, sex, marital status and comorbidities), clinical diagnosis, procedures and operations, costs, complications and hospital characteristics will be all extracted from the HQMS database. Medical insurance, including Urban Employee-Based Medical Insurance (UEBMI), Urban Resident-Based Medical Insurance (URBMI) and New Cooperative Medical Scheme (NCMS), self-pay and others (e.g., commercial insurance) will be identified in our study. Preexisting comorbidities will be extracted. The Charlson Comorbidity Index (CCI) will be calculate and categorized. Investigators will also extract the indication for KA. Hospital characteristics, such as region, volume of surgery will be extracted.

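### Do the undefined comparison groups, with only two-group tests named for continuous variables, call for a change to the analysis plan?

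*Combined protocol and SAP*

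**What the plan says.** The Statistical analysis section mentions group comparisons twice. The first is unadjusted: "Basic information in different groups will be compared". The second is adjusted: propensity-score matching or multivariable regression will be used to "compare the incidence of complications and resource utilization in different groups". Neither sentence, nor any other section, says what the groups are.

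For continuous variables the rule is "Mann-Whitney U test will be used for non-normally variables and Student t-test will be used for normally variables". For categorical variables it is "chi-square test or Fisher's exact test will be used for categorical data". Significance is set at P < 0.05, with no statement on sidedness or multiplicity. Between the two group comparisons stands a multivariable logistic regression for risk factors of complications.

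Two classifications elsewhere in the document clearly have more than two levels. Under Measurement of outcomes: "Five types of JA of our interest will be identified in HQMS, including KA, HA, SA, EA and AA". Under Study variables, three public insurance schemes are listed, and then "self-pay and others (e.g., commercial insurance) will be identified in our study", which makes five insurance categories. Hospital region, surgical volume, Charlson category and year of surgery may also have several levels.

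**The concern.** The Student t-test and the Mann-Whitney U test each compare exactly two groups. If the groups were the five joint types or the five insurance categories, the plan would name no unadjusted test for age or costs. An analyst who kept to the named tests might run them pair by pair at 0.05, and the chance of a false positive somewhere in the set would rise well above 0.05.

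The second worry is about the adjusted comparison. The data are retrospective, and if the contrast to be matched or modelled is not named in advance, it could be chosen after results are seen. Standard propensity-score matching is also ordinarily a two-group method, so the missing definition touches one of the two adjusted options as well.

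**Working it through.** The plan gives no sample size, power or event count, so it has no figure of its own to reproduce. The check has two parts.

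**1. How large the problem would be under pairwise testing**

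Inputs: alpha 0.05 from the plan; two-sided testing, large samples, equal groups and no true differences are assumptions. With k groups there are k(k − 1)/2 pairs. The chance that at least one pair is significant is the upper tail of the studentised range for k groups at 1.96 × √2 = 2.77, with very large degrees of freedom.

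| Groups k | Pairs | Chance of at least one false positive | If tests were independent, 1 − 0.95^pairs |
|---|---|---|---|
| 2 | 1 | 0.050 | 0.050 |
| 3 | 3 | 0.122 | 0.143 |
| 4 | 6 | 0.203 | 0.265 |
| 5 | 10 | 0.286 | 0.401 |

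The third column is the relevant one, because pairs share groups and are correlated.

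Unequal group sizes lower the five-group figure somewhat. Sizes of 1500:1000:100:10 for knee, hip, shoulder and elbow, with ankle assumed at 1 to 10, give 0.22 to 0.23 by simulation. This ratio is only illustrative: it comes from the Introduction, where the knee, hip and shoulder volumes are worldwide but the elbow figure is "more than 10 thousand elbow arthroplasties (EA) in Germany". Three assumed insurance splits (60/15/15/5/5, 40/20/25/10/5 and 30/20/30/10/10) give 0.27 to 0.28. Four tests against a single reference give about 0.16 with equal groups. With knee as reference and sizes 1500:1000:100:10:5, they give about 0.185.

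On simulated lognormal data in five groups, pairwise Mann-Whitney tests gave 0.27 to 0.28 and one Kruskal-Wallis test gave 0.048 to 0.051. The usual multi-group test therefore removes the inflation.

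**2. Whether the plan leads there**

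- *Unadjusted comparison.* The sentence on basic information is followed by the tests and then directly by the logistic model for complications. Complications are extracted under Study variables and analysed under Measurement of outcomes. Comparing patients with and without a complication before modelling that outcome is a natural reading. It gives two groups (first row of the table), and the named tests are right.
- *Five joint types.* The plan analyses all five, but that does not mean testing them against one another. Two groups can be compared within each joint type.
- *Multi-level factors.* Chi-square, Fisher's exact test and regression all accept more than two levels. Only unadjusted tests of continuous variables are affected. Costs can go through the adjusted regression that the plan already names.
- *Pairwise testing.* No sentence proposes testing all pairs, or testing each level against a reference.

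The rates above 0.05 in part 1 therefore need two things that the plan does not state: a grouping with more than two levels, and unadjusted pairwise testing of it.

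**The case for a change.** The strongest case for acting is that the text really is silent, that five-level classifications are prominent in it, and that naming the groups would take two or three sentences. The complication yes/no reading is plausible but not proved. The adjusted comparison of complications and resource utilization is a stated aim, and matching cannot be set up until someone decides what is matched with what. With data already collected, naming the contrast beforehand is the main protection against selecting it afterwards. Nor does a very large database reduce false positives under a true null.

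Much of this stands as description: the groups are undefined in both places, and a sentence naming them would make the plan easier to follow. It does not show that anything in the plan is wrong. With two groups nothing changes. With more than two, the analyst is not forced to choose between breaking the plan and testing pairs at 0.05, since two-group comparisons within a joint type and the stated regression are both open. One-way ANOVA or Kruskal-Wallis is the ordinary choice for an unadjusted table with several columns. Adjusted pairwise procedures or standardised differences would be additions of preference, not cures for a demonstrated error. Exact equality of all groups is also a poor guide here: the database holds about 230 million records, so trivial differences are likely to reach P < 0.05 whichever test is used.

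**Conclusion.** No change follows. The plan leaves out a detail, namely the comparison groups and a test for continuous variables in more than two of them, and an analyst would fill it in the usual way. The effect is nil if the groups are binary. It would reach about 0.29 per continuous variable for five equal groups, or 0.22 to 0.28 for the unequal sizes tried, only under unadjusted testing of all ten pairs, which the plan does not propose. These figures assume two-sided tests, large samples and no true differences, and the unequal sizes are illustrative. The test-choice issue is confined to unadjusted comparisons of continuous variables; the logistic risk-factor models do not depend on it. In the adjusted comparison the groups are equally unnamed, but regression takes a factor with any number of levels, and matching obliges the analyst to specify its two groups before it can be run.

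### The plan names the Student t-test with no equal-variance condition, so P values for unadjusted two-group comparisons can be wrong if the groups differ in both size and SD

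*Combined protocol and SAP*

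**What the plan says.** In the Statistical analysis section, the unadjusted comparison is introduced with "Basic information in different groups will be compared". The groups are not defined. For continuous variables the rule is "Mann-Whitney U test will be used for non-normally variables and Student t-test will be used for normally variables", with significance at P < 0.05 in SAS 9.4. Sidedness is not stated. Neither a variance check nor a Welch or Satterthwaite version is mentioned anywhere in the document.

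The same section plans confidence intervals only for the logistic regression, "with the calculation of odds ratios (ORs) and 95% confidence interval (CI". Outcome comparisons are handled separately: "the propensity-score matching or multivariable-adjusted regression will be performed to compare the incidence of complications and resource utilization in different groups".

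The document gives no group sizes. Under Measurement of outcomes it says "Five types of JA of our interest will be identified in HQMS, including KA, HA, SA, EA and AA". The only volumes by joint type that bear on relative size are annual worldwide figures in the Introduction: "more than 1.5 million knee arthroplasties (KA") and "over 100 thousand shoulder arthroplasties (SA").

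**The concern.** Student's t-test rests on normality and on equal variances. The plan's rule attends only to the first. The equal-variance assumption matters little when the groups are of similar size and a great deal when they are not. In a national database spanning common and rare joint replacements, groups of similar size cannot be taken for granted.

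If the smaller group is the more variable one, the pooled standard error is too small and differences are declared too often. If it is the less variable one, the pooled standard error is too large and real differences can be missed. The bias depends on the ratio of sizes and the ratio of SDs, not on total n, so a large database does not remove it.

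**Working it through.** The plan states no sample size, power or error rate for these comparisons, so there is no figure to reproduce.

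**Inputs**
- Test: pooled-variance Student t-test, from the Statistical analysis section.
- Significance level: 0.05, from the same section. Two-sided is my assumption.
- Size ratio r (larger/smaller group): 1,500,000 / 100,000 = 15, from the worldwide volumes in the Introduction. This is a proxy, not a study count.
- SD ratio k (smaller/larger group): not in the document. Assumed, 0.67 to 1.5.

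**Formula.** Let the larger group have SD s and size r·n, and the smaller group SD k·s and size n. In large samples:
- true SE² = s²/(rn) + k²s²/n = s²(1 + rk²)/(rn)
- pooled SE² = [s²(r + k²)/(r + 1)] × [(r + 1)/(rn)] = s²(r + k²)/(rn)
- true SE / pooled SE = √[(1 + rk²)/(r + k²)]
- true error of the nominal 5% test = 2[1 − Φ(1.96 × pooled SE / true SE)]

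The group size n cancels from the ratio, which is why more patients do not help. If k = 1 the ratio is 1 for any r. If r = 1 it is 1 for any k. Both kinds of inequality are needed.

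**Numbers at r = 15**
- k = 0.8: √(10.6 / 15.64) = 0.823; 1.96 / 0.823 = 2.38; error 1.7%
- k = 1: ratio 1; error 5.0%
- k = 1.25: √(24.4375 / 16.5625) = 1.215; 1.96 / 1.215 = 1.61; error 10.7%
- k = 1.5: √(34.75 / 17.25) = 1.419; 1.96 / 1.419 = 1.38; error 16.7%

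**Range.** At 15:1, SD ratios of 0.9 and 1.11 already give 3.2% and 7.4%. At 1.5:1, SD ratios from 0.67 to 1.5 give 3.4% to 7.0%. At 1:1 the error is 5.0% throughout.

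**Simulation.** With normal data, equal means, 200,000 replicates per setting and 15:1 sizes, the rejection rates were:

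| Sizes | SD ratio | Student | Welch |
|---|---|---|---|
| 1,500 / 100 | 0.8 | 1.7% | 4.9% |
| 1,500 / 100 | 1.25 | 10.8% | 5.1% |
| 1,500 / 100 | 1.5 | 16.8% | 5.0% |
| 150,000 / 10,000 | 0.8 | 1.7% | 5.0% |
| 150,000 / 10,000 | 1.25 | 10.7% | 5.0% |
| 150,000 / 10,000 | 1.5 | 16.7% | 4.9% |

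Student's error is the same at a hundred times the sample size. Across all the settings simulated, with SD ratios from 0.67 to 1.5, Welch stays between 4.9% and 5.1%.

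**When it would change a conclusion.** Assume age SDs of 10 in the larger group and 12.5 in the smaller.
- At 150,000 v 10,000, the pooled SE is √[103.516 × (1/150,000 + 1/10,000)] = 0.105 and the true SE is √(100/150,000 + 156.25/10,000) = 0.128. A one-year difference gives z of about 9.5 (pooled) or 7.8 (Welch), with the same conclusion. The tests disagree only for observed differences between 1.96 × 0.105 = 0.21 and 1.96 × 0.128 = 0.25 years.
- At 1,500 v 100, both SEs are ten times larger, so the tests disagree between about 2.1 and 2.5 years.

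**The case against.** A reader might infer that unequal group sizes alone make these P values wrong. They do not: with equal SDs the test holds 5% at any imbalance, and the document gives no SDs. Every error rate above other than 5% rests on an assumed SD ratio.

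A reader might also take 15:1 as the study's own imbalance. It is a quotient of two worldwide background volumes. The plan does not say that knee will be t-tested against shoulder, and a comparison across all five joints would not be a two-sample t-test at all. Marked imbalance is plausible but inferred.

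Nor does the text support a claim that reported intervals will be too narrow or too wide, since intervals are planned only for odds ratios.

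The reach is small. Under Study variables most items are categorical, the Charlson index is to be categorized, and costs are plausibly skewed and would go to the rank test; age is the one plainly continuous demographic named. Risk factors for complications go to logistic regression, and outcome comparisons to matching or adjusted regression. With 1:1 matching the pooled and Welch standard errors would coincide, though no matching ratio is stated. In very large groups the choice will seldom alter a conclusion.

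Finally, the authors may use the test's name generically, with no thought of a variance option.

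All of this limits the consequence, and I accept it. It does not remove the gap: the text names a test whose validity depends on an unstated condition. If the name is meant generically, the reader cannot tell which result will be reported.

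**Conclusion.** The point holds in conditional form and is minor. As written, "Student t-test will be used for normally variables" is unconditional on variance. If the groups differ in both size and SD, P values can err in either direction, and sample size does not cure it. At the illustrative 15:1 ratio, assumed SD ratios of 0.8 to 1.5 move the true error of a nominal 5% test from 1.7% to 16.7%.

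The effect is confined to unadjusted two-group comparisons of normally distributed basic information. It is most likely to matter where one group is small, such as a rare joint type. The logistic odds ratios are unaffected, and the document gives no basis for saying that any outcome conclusion depends on this choice.

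**What to change.** In the Statistical analysis section, replace the Student t-test with the *Welch (unequal-variance, Satterthwaite) t-test* for two-group comparisons of means.

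The cost is a phrase of text. No new data or software is needed, because PROC TTEST in SAS already prints the Satterthwaite result. At these sizes, the loss of power when the variances are in fact equal is negligible.

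### Must the plan say whether the complication models pool the five joints, and what happens if an odds ratio cannot be estimated?

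*Combined protocol and SAP*

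**What the plan says.** The Introduction defines JA collectively as the five joints. Measurement of outcomes then states: "Epidemiological characteristics, risk factors, complications and resource utilization of these five types of JA will be analyzed". The Statistical analysis section gives a single general description of the model: "multivariable-adjusted logistic regression will be performed to examine the risk factors of complications following JA". Its factors are introduced by an e.g. and are "year of surgery, patient demographics and region of hospitals". Results are to be odds ratios with 95% confidence intervals.

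Three further points bear on the reading. Study variables lists procedures and operations among the extracted data, so the joint operated on is known for every patient. The same section extracts a surgical indication for knee arthroplasty only. Fisher's exact test is provided for comparing categorical data between groups, and propensity-score matching is offered against confounding; neither is a provision for a sparse logistic model.

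The documents state no sample size, number of events, complication rate or case count by joint.

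**The concern.** Read with the Introduction's definition, the model statement describes one regression over all five joints. Read with Measurement of outcomes, it describes five. If risk factors act differently in different joints, the two give different answers. A pooled model without joint-by-factor interactions returns one average odds ratio per factor, weighted towards the joints that contribute most events. A reader could take that average as applying to elbow or ankle surgery. If joint type were also left out, a factor more common in the higher-risk joint would pick up a spurious association.

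Separate models carry the opposite risk. With few events in a low-volume joint, a category may have none, and its odds ratio then has no finite maximum-likelihood estimate. With neither choice written down, both could be made after the data have been seen, and these data already exist.

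**Working it through.** There is no figure in the plan to reproduce, so the check asks how much each choice could matter and whether the documents show that it would. I recalculated all the results below.

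**1. Weight of each joint if pooled.** The Introduction's background volumes, each a minimum, are knee 1.5 million, hip 1 million and shoulder 0.1 million (worldwide) and elbow 0.01 million (Germany only). No ankle volume is given.

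- Total: 1.5 + 1.0 + 0.1 + 0.01 = 2.61 million.
- Knee plus hip: 2.5/2.61 = 95.8%. Shoulder: 3.8%. Elbow: 0.4%.
- With elbow 0.10 and ankle 0.05 million assumed: 2.5/2.75 = 90.9%.

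These are not counts from the study database, and a pooled odds ratio is weighted by information (largely events), not by procedures.

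**2. Effect of pooling.** A logistic model with joint type as a main effect was fitted to expected counts, for a binary factor with 30% prevalence. Ankle is left out. All odds ratios and risks are assumed.

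| Assumed truth | Pooled OR |
|---|---|
| Elbow OR 3.0, others 1.2, equal risk (0.5%, 1% or 5%), elbow 10,000 | 1.21 |
| Same, elbow risk 5%, others 1% | 1.23 |
| Elbow 100,000, equal risk | 1.26 to 1.27 |
| Elbow 100,000, elbow risk 5%, others 1% | 1.46 |
| Knee OR 0.80, hip 1.25, others 1.0; hip risk 1, 2 or 3 times knee | 0.98, 1.05, 1.09 |

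**3. Joint type omitted.** Two joints, knee to hip 1.5:1, knee risk 1%, a factor with no effect in either joint and prevalence 30% or 50% in knee.

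| Excess prevalence in hip | Hip risk 1.5 times knee | 2 times | 3 times |
|---|---|---|---|
| 10 points | 1.04 to 1.05 | 1.07 to 1.08 | 1.12 to 1.13 |
| 20 points | 1.09 | 1.16 | 1.25 to 1.26 |

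With joint type in the model, every entry is 1.00. The plan does not say that joint type will be omitted.

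**4. A category without events in a separate model.** If a category is expected to hold a share s of E independent events, the chance that it has none is (1 − s)^E.

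| s | E = 10 | E = 20 | E = 50 |
|---|---|---|---|
| 3% | 74% | 54% | 22% |
| 8% | 43% | 19% | 1.5% |
| 15% | 20% | 4% | 0.03% |

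For region, Data source mentions 31 provincial-level regions. If all 31 entered as equal-sized levels and risk were 1% (both assumed), the expected number without an event is 31 × 0.99^(N/31): about 16 for N = 2,000 cases of a joint, 1.2 for N = 10,000, and none for N = 100,000. The plan does not say that region will enter at 31 levels.

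**5. What the text supports.** The phrase about the five types in Measurement of outcomes leans towards results by joint. The knee-only indication leans the same way: it fits a knee model and cannot readily enter a pooled one. If a pooled model is fitted instead, the open factor list allows joint type, and the procedure codes supply it. Nothing in the plan forbids the sensible version of either approach.

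**The case for a change.** The strongest case for a change is that these are existing records, so a written specification is the main protection against choices made on sight of the results. An open factor list leaves the choice open too, and Measurement of outcomes states what will be reported, not how it will be modelled. Opposing effects in knee and hip, the two dominant joints, would average to near 1 whatever the volumes of the rarer joints. A sentence or two would settle the matter at almost no cost, and SAS 9.4 already offers a penalised-likelihood option for separation.

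Most of this stands as an argument for good practice. The omissions are real: no section states the fitting strategy or a fallback. What does not stand is the step from an omission to an error. The readings differ in result only if effects differ between joints, which is assumed. A claim that a pooled estimate would reflect little besides knee and hip is too strong, since a larger elbow volume with higher elbow risk moved it from 1.2 to 1.46.

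The remedies are not free either. Interactions with joint type need up to four terms for a binary factor, but up to 4 × 4 = 16 for the five insurance categories and 4 × 30 = 120 for 31 regions. They bring back the thin elbow and ankle cells that pooling avoids. Penalised likelihood is one of several accepted responses to separation, alongside exact logistic regression, collapsing categories, or reporting that an odds ratio is not estimable.

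**Conclusion.** No change to the plan is needed. The plan leaves the fitting strategy and the handling of separation unwritten, but no rule it does state gives a wrong result, and its own wording points analysts towards a reasonable choice. The possible size, a pooled odds ratio of 1.21 to 1.46 where the elbow value is 3.0, or up to 1.26 for a null factor if joint type were ignored, rests wholly on assumed effects, risks and volumes. Separation is plausible for a low-volume joint or a very rare complication. It cannot be shown from the documents, and it is unlikely for a high-volume joint unless the complication is very rare.

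The study is a retrospective description of a database with no stated primary hypothesis. An ordinary report would label each model as pooled or joint-specific, give its event count, describe pooled odds ratios as averages over joints, and name any method used where an estimate failed. The conclusion would change if the plan excluded joint type from a pooled model, or if counts by joint showed that the intended models could not be fitted; the documents show neither.

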## **Methods**

### **Data source**

This nationwide retrospective study will be a review of the HQMS database. The HQMS database is a mandatory electronic inpatient database system developed by the National Health Commission of the People's Republic of China. Since 2013, tertiary hospitals have been required to upload their inpatient discharge records. By 2019, the HQMS database has included about 230 million standardized inpatient discharge records of more than 1,000 hospitals across all 31 provincial-level administrative regions in mainland China. Patient demographics, clinical diagnosis, procedures and operations, costs and complications are all recorded in the HQMS database. The diagnosis is coded in the form of International Classification of Diseases, Tenth Revision (ICD-10), and the procedures and operations are coded in accordance with International Classification of Diseases, Ninth Revision, Clinical Modification (ICD-9-CM). A more detailed description of this database can be found in previous studies. This study was authorized by the HQMS Committee Board and approved by the institutional review board, with waiver of informed consent.

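### No method is stated for within-hospital correlation: if residual risk differs between hospitals and region effects are meant to generalise, ordinary logistic regression gives region CIs that are too narrow

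*Combined protocol and SAP*

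**What the plan says.** For risk factors, the Statistical analysis section plans a multivariable logistic regression to examine the "risk factors of complications following JA (e.g., year of surgery, patient demographics and region of hospitals". Region of hospitals is one of the example factors, odds ratios are reported with 95% CIs, and the significance threshold is P < 0.05.

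For group comparisons, the same section says that "the propensity-score matching or multivariable-adjusted regression will be performed to compare the incidence of complications and resource utilization in different groups". The groups are not defined.

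The Data source section describes records from "more than 1,000 hospitals across all 31 provincial-level administrative regions in mainland China". The Study variables section adds: "Hospital characteristics, such as region, volume of surgery will be extracted". Volume is therefore collected, but it is not named as a model term. Measurement of outcomes lists five joint types (knee, hip, shoulder, elbow, ankle) to be analysed.

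No section mentions a hospital random or fixed effect, GEE, a cluster-robust variance, or any other way of handling patients who share a hospital.

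**The concern.** Region is a property of the hospital. All patients of one hospital share its value, so the information about a region contrast is limited by the number of hospitals in each level as well as by the number of patients. A model-based standard error from ordinary logistic regression counts patients as independent and leaves out the variation between hospitals.

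Some regional differences could then be reported as significant when they reflect only which hospitals happen to lie in each region. The Introduction offers the results to healthcare planners, so a spurious regional difference could be acted on. The same applies to surgical volume if it is entered in the model.

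The adjustment steps in the plan do not remove the problem. Covariates and propensity-score matching deal with confounding; they do not supply a variance that allows for the remaining correlation within hospitals.

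**Working it through.** The documents give no sample size, event count, complication rate, cases per hospital or intraclass correlation (ICC), so there is no figure of the plan's own to reproduce. The check asks how large the effect could be over a range of assumed inputs.

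**Inputs from the documents.** At least 1,000 hospitals (1,000 used); 31 provincial-level regions; significance level 5%, taken as two-sided to match the 95% CI.

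**Assumed inputs.** Complication risk 2%; SD of hospital log-odds after adjustment 0.1 or 0.5; mean cases per hospital m = 20, 100 or 300; coefficient of variation (CV) of hospital size 0 or 1; region level holding 300 of the 1,000 hospitals.

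**Step 1, ICC.** With normal hospital intercepts on the logit scale, centred so that the average risk p is 2%, ICC = Var(hospital risk) / [p(1 − p)]. Numerical integration gives 0.0002 at SD 0.1 and 0.00543 at SD 0.5.

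**Step 2, design effect for region.** DEFF = 1 + [m(1 + CV²) − 1] × ICC. The naive standard error is too small by a factor of √DEFF, and the true type I error is 2 × [1 − Φ(1.96/√DEFF)]. For example, at SD 0.5, m = 100 and CV 0: DEFF = 1 + 99 × 0.00543 = 1.54, √DEFF = 1.24, type I error 11.4%. With CV 1: DEFF = 1 + 199 × 0.00543 = 2.08, √DEFF = 1.44, type I error 17.4%.

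| Mean cases | DEFF at SD 0.5, CV 0 / CV 1 | Type I error, formula | Type I error, simulation |
|---|---|---|---|
| 20 | 1.10 / 1.21 | 6.2% / 7.5% | 6.3% / 7.4% |
| 100 | 1.54 / 2.08 | 11.4% / 17.4% | 10.9% / 16.9% |
| 300 | 2.62 / 4.25 | 22.6% / 34.2% | 23.6% / 33.6% |

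The simulation column is a Monte Carlo run under a null region effect, with 6,000 replicates per setting. Separate runs gave 11-18% at 100 cases and 22-34% at 300.

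**Step 3, little variation.** At SD 0.1 and m = 300, DEFF is 1 + 299 × 0.0002 = 1.06 (CV 0) or 1 + 599 × 0.0002 = 1.12 (CV 1), so type I error is 5.7% or 6.4%. Simulated values over all three means were 4.7-7.0%.

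**Step 4, other risks.** At m = 100, SD 0.5 and CV 0, simulated type I error is 6.6% at a risk of 0.5%, 8.3% at 1% and 19.2% at 5%.

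**Step 5, patient factors.** Here the ICC in DEFF is multiplied by the ICC of the factor itself, which is also unknown. At 2% risk, m = 100 and SD 0.5 (CV 0 to CV 1), type I error is 5.1-5.2% for a factor ICC of 0.02, 5.3-5.6% for 0.05 and 6.3-7.6% for 0.2. For a factor balanced within hospitals, simulation gave 4.1-5.8% over all settings run.

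**Step 6, does the remedy work?** The ranges here are minimum to maximum over the settings run.
- Uncorrected sandwich, z reference, 300 of 1,000 hospitals in the level: 4.7-5.9%.
- Uncorrected sandwich, 32 of 1,000 hospitals (1,000 / 31 ≈ 32, the average if region means province): about 5-9%.
- Uncorrected sandwich, 5 of 150 hospitals (an assumed case for a rarely performed joint type): about 6-23%.
- Bias-corrected sandwich with t reference: 4.4-6.0% with 32 hospitals; 1.9-4.9%, which is conservative, with 5.
- Hospital random intercept at SD 0.5: 4.1-5.9% with 300 hospitals, 4.6-5.4% with 32, 3.7-4.9% with 5. The simulated intercepts were normal, so this model was correctly specified.
- Matched comparisons, 100 cases per hospital, one assumed group-membership ICC of 0.2: variance clustered by hospital alone gave 4.8-5.3% for complications and 3.8-4.3% for log cost.

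**The case against.** The strongest reply is that the plan is brief and names no variance estimator, so silence is not a decision to treat patients as independent. That is right as far as it goes: a reader might infer that the plan prescribes an uncorrected analysis, and the documents show only that the method is unstated. However, logistic regression with no further qualification is ordinarily fitted with independent observations. If the method is left open, it can be chosen after the results are seen.

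A second reply concerns the inference target. Tertiary hospitals are required to upload their discharge records. If region effects only describe what happened in these hospitals in these years, differences between hospitals are part of the quantity described and not sampling noise. This stands as a condition on the point. The plan does not state its target, although CIs, P values and the stated use by planners in China and similar countries suggest a wider one.

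Third, a reader might infer that a definite share of the region findings will be false, that patient-level results are badly affected, or that matched analyses need variance for both hospital and pair. The documents support none of these. They give no ICC, risk or case numbers; patient factors are affected only in so far as they cluster by hospital; and clustering by hospital alone already controlled error in the matched simulations. Those simulations used a single assumed ICC of 0.2 for group membership, so they are illustrative only.

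Finally, the coding of region is not stated. Province coding, and with it the figure of 32 hospitals per level, is an assumption.

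**Conclusion.** The point holds conditionally and should be fixed. The direction is clear if two conditions are met: region effects are meant to generalise beyond the hospitals and years observed, and complication risk varies between hospitals after adjustment. Ordinary logistic regression then gives CIs that are too narrow and P values that are too small for region, and for volume if it is entered. Odds ratio estimates are little affected.

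The size is unknown. It depends on the product of cases per hospital and ICC, and both may differ between the five joint types. In the assumed scenarios it runs from negligible (few cases, or SD 0.1) to a type I error several times the nominal 5% (300 cases per hospital, SD 0.5). These figures show what is possible and do not predict this study's error rate. Confidence is high that no method is stated and medium that the effect matters here.

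**What to change.** Add to the Statistical analysis section that the complication and resource-use regressions account for clustering by hospital, and that all 95% CIs and P values rest on this.

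- Name one primary method in advance: for example a hospital random intercept (PROC GLIMMIX with quadrature), or GEE or cluster-robust variance with hospital as the cluster (PROC GENMOD or PROC SURVEYLOGISTIC).
- If a sandwich variance is chosen, apply a small-sample correction with a t reference to all region contrasts. The uncorrected form is already anticonservative at about 32 hospitals in a level, so a rule that applies the correction only when hospitals are few would not be enough.
- For propensity-matched comparisons, use a variance clustered at least by hospital. Two-way variance for hospital and pair is optional.
- State whether region effects are meant to generalise beyond the hospitals and years observed, and how region is coded.

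The cost is a few sentences and a little more analysis work in SAS 9.4, which is already planned; the small-sample correction may need extra programming. No new data are needed. Where hospital variation exists, CIs for hospital-level factors will widen and some region effects may lose significance. With about 5 hospitals in a level the corrected sandwich is conservative. Results for factors balanced within hospitals will hardly change.
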